4.4.3 Device Application Environment

REGENETEN System is intended for use by trained medical professionals in a hospital or clinical environment (equivalent to an orthopaedic operating room). The components in REGENETEN instrument kit will be used in a sterile environment.

All REGENETEN components (bioinductive implant, bioinductive implant delivery system, tendon marker, tendon stabilizing guide, manual placement instruments, bone anchors and tendon anchors) are provided sterile, non-pyrogenic, for single-use only, and are packaged in a dual sterile seal, tray-in-tray configuration as described in Instructions for Use (IFUs) and surgical technique documents provided by Smith+Nephew [25, 26, 27, 28, 29, 30, 31].

4.4.4 Potential Adverse Effects

As with any surgery, this surgery will cause risks. Potential complications of this type of surgery include but are not limited to anesthesia complications; incision healing problems; trauma and bleeding; infection; failure of the repair or retear; nerve damage; vascular damage; pain or stiffness that persists; tissue inflammation.

Warnings and Precautions stated in the IFU:

Bioinductive Implant:

- Do no reuse or re-sterilize.
- Do not use if the product package is damaged or opened.
- The Bioinductive Implant should not be applied until bleeding and infection are controlled.
- Application of the Bioinductive Implant does not modify the postoperative treatment. The surgeon must determine motion and strength requirements according to standard practice.

CONFIDENTIAL AND PROPRIETARY

Study Protocol	Smith-Nephew
A Prospective, Multi-center, Randomized Controlled	Number:
Study to Evaluate the Safety and Efficacy of ARCR	REGENETEN.2020.01
ı	Version: 2, 08 Dec 2021
System in Full-thickness Tears (large or massive) Repair versus ARCR alone	Page: 25 of 134

Tendon Anchors:

- Do not use if the temperature indicator on the product packaging is black.
- Do not use if the product package is damaged or opened.
- Do not reuse or re-sterilize.
- Excessive force applied during anchor deployment may result in damage to the tissue, to the material being fixated, to the anchor.
- Overlapping anchors may result in damage to the anchor.

Bone Anchors:

- Do not use if the product package is damaged or opened.
- Do not reuse or re-sterilize.
- Excessive force applied during anchor deployment may result in damage to the tissue, to the material being fixated, to the anchor.
- Inserting the Bone Anchor through excessive soft tissue and failing to engage the anchor into bone may not provide adequate fixation.

Bioinductive Implant Placement Cannula:

- Do not use if the product package is damaged or opened.
- Do not reuse or re-sterilize.
- The cannula should be tapped lightly when inserting into bone. Do not drive the frame that holds the Bioinductive Implant into the bone.
- Do not advance cannula against resistance or damage to device may occur.

Manual Placement Instruments:

- Do not use if the product package is damaged or opened.
- Do not reuse or re-sterilize.

CONFIDENTIAL AND PROPRIETARY

Study Protocol	Smith-Nephew
A Prospective, Multi-center, Randomized Controlled	Number:
Study to Evaluate the Safety and Efficacy of ARCR	REGENETEN.2020.01
augmented with REGENETEN™ Bioinductive Implant	Version: 2, 08 Dec 2021
System in Full-thickness Tears (large or massive) Repair versus ARCR alone	Page: 26 of 134

- Excessive force applied during Bone Anchor deployment may result in damage to the material being fixated or to the anchor.
- Positioning the Bioinductive Implant with the Bone Anchor Inserter nubs may result in damage to the Bioinductive Implant.
- Driving the Bone Punch with a mallet before the bone punch is engaged with the Bone
 Anchor Inserter may result in an inability to advance the Bone Anchor into the holes.

Tendon Stabilizing Guide:

- Do not use if the product package is damaged or opened.
- Do not reuse or re-sterilize.
- The guide wire should be tapped lightly when inserting it into bone. Do not drive the shaft
 of the Tendon Stabilizing Guide into the bone.
- The tip of the guide wire is sharp. Take proper care for handling and disposal of a sharp instrument.

Tendon Marker:

- Do not use if the product package is damaged or opened.
- Do not reuse or re-sterilize.
- The Tendon Marker is sharp. Take proper care for handling and disposal of a sharp instrument.

Tendon Marker and Tendon Stabilizing Guides are not mandatory to be used.

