- 13. Subjects with condition(s) that contraindicate or complicate outcomes of ARCR e.g., > Hamada 3 rotator cuff arthropathy on X-ray, Goutallier atrophy > Grade 3, proximal humeral fracture or scapular fracture, avascular necrosis of the humeral head or glenoid, history of immunodeficiency disorders, history of chronic inflammatory disorders, oral or injected steroid use in last 4 weeks;
- 14. Subjects who are pregnant or breast feeding;
- 15. Subjects who are currently involved in any injury litigation or workers compensation claims;
- 16. Subjects who are enrolled, or plan to enroll, in another clinical trial during this study that would affect the outcomes of this study;

Study Protocol	Smith-Nephew
A Prospective, Multi-center, Randomized Controlled	Number:
Study to Evaluate the Safety and Efficacy of ARCR	REGENETEN.2020.01
augmented with REGENETEN™ Bioinductive Implant	Version: 2.0, 08 Dec
System in Full-thickness Tears (large or massive) Repair	2021
	Page: 9 of 134

	17. Subjects with a history of noncompliance with medical treatment, physical therapy (PT)/rehabilitation, or clinical study participation;
	18. Subject who, in the opinion of the Investigator, has an emotional or neurological condition that would pre-empt their ability or willingness to participate in the study including mental illness, mental retardation, and drug or alcohol abuse;
	 Subjects who do not meet the indication or are contraindicated according to specific Smith+Nephew REGENETEN System's Instructions for Use (IFUs);
	20. Subject that meets the definition of a Vulnerable Subject per ISO14155:2020 Section 3.44.
Study Duration:	48 months (24 month enrollment period and 24 months follow-up period).
Primary Endpoint:	The cumulative 6 months retear rate after full-thickness ARCR augmented with REGENETEN versus ARCR alone. Failure is defined as Sugaya Type IV or V retear/recurrence (full-thickness discontinuity seen on both coronal and oblique sagittal MRI images).
Secondary Endpoint(s):	 The cumulative 3, 12, and 24 months retear rate after full-thickness ARCR augmented with REGENETEN (confirmed on MRI) versus ARCR alone; Overall performance of full-thickness ARCR augmented with REGENETEN versus ARCR alone at Baseline and at 3, 6, 12 and 24 months assessed by:
	 Oxford Shoulder Score (OSS), Western Ontario Rotator Cuff (WORC)/Chinese version WORC (C-WORC) Index, Constant-Murley Score (CM),

Study Protocol	Smith-Nephew
A Prospective, Multi-center, Randomized Controlled	Number:

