Safety Data	 All adverse events (AEs) and complications occurring from the time of subject enrollment until study termination or study completion including intra-operative adverse events and complications; Device Deficiencies (DD) 					

	Study Protocol	Smith
Ī	A Prospective, Multi-center, Randomized Controlled Study to Evaluate the	Number: REGE

A Prospective, Multi-center, Randomized Controlled Study to Evaluate the Safety and Efficacy of ARCR augmented with REGENETEN™ Bioinductive Implant System in Full-thickness Tears (large or massive) Repair versus ARCR alone

Version: 2.0, 08 Dec 2021

Page: 12 of 134

STUDY SCHEDULE

Schedule of Event	Screening (Baseline) Day -60 to Day -1	Operation Day 0	2 Weeks Follow- up 14 ± 5 Days	6 Weeks Follow- up 42 ± 7 Days	3 Months Follow- up 91 ± 15 Days	6 Months Follow- up 182 ± 30 Days	N F UJ
Informed Consent	X ¹						
Inclusion/Exclusion	X ²	X ²					
Demographics/Medical History/BMI	Х						
Operative/Discharge Data		X					
Oxford Shoulder Score	Х				Х	Х	
WORC/C-WORC	X				Х	Х	
Constant-Murley Score	X				Х	Х	
Subjective Shoulder Value	X				X	Х	
EQ-5D-5L	Х				Х	Х	
Patient Satisfaction	X				Х	Х	
VAS Pain Score	X		X	X	X	Х	
Return to Work Questionnaire	Х		X ³	X ³	X ³	X ³	
Opioid Use			X ⁴				
Reoperation			X	Х	Х	Х	
MRI Assessment	X ²				Х	Х	
Concomitant Medication/Therapy	Х	Х	Х	Х	Х	Х	
Safety Assessment (AEs, DDs)		X	Х	Х	Х	Х	
End of Study/Exit		X ³	X ³	X ³	X ³	X ³	

¹ Date of Informed consent may be the same day or another day before screening giving the subject enough time to consider particip. ² Inclusion/exclusion confirmation will be performed at the time of screening and study procedure to confirm subject meets eligibility or be confirmed on arthroscopy using a calibrated probe. X-Ray and MRI to confirm eligibility criteria must be within 12 months of surge ³ As appropriate.

CONFIDENTIAL AND PROPRIETARY

This document contains information that is confidential and proprietary to Smith+Nephew PLC and Smith+Nephew, Inc. and is intended for use only manufacturer. It shall not be reproduced or copied in whole or in part, nor shall the contents be disclosed by any means without prior written permission or shall anyone make any use of it that is contrary to the expressed or implied wishes of Smith+Nephew.

TMP-CD-05-01 – Clinical Protocol-Device – Revision D.1; SOP-CD-05 Clinical Protocols

⁴ Opioid use will be documented daily from day 0 to day 14.

Study Protocol	Smith-Nephew

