10.2 ANALYSIS POPULATIONS

The following study populations and analysis sets will be defined.

- Full analysis set (FAS): following the Intention to Treat principle including all randomized patients who were recruited into the study and attended at least one post-surgery assessment. This analysis population includes all randomized patients in the groups to which they were randomly assigned, regardless of their adherence with the entry criteria, regardless of the treatment they actually received, and regardless of subsequent withdrawal from treatment or deviation from the protocol.
- Per protocol set (PP): including all patients in the full analysis set who have no significant protocol deviations and met the inclusion/exclusion criteria.
- Safety analysis set (SAF): including all patients who have received the study device.

CONFIDENTIAL AND PROPRIETARY

Study Protocol	Smith-Nephew
A Prospective, Multi-center, Randomized Controlled	Number:
Study to Evaluate the Safety and Efficacy of ARCR	REGENETEN.2020.01
augmented with REGENETEN™ Bioinductive Implant	Version: 2.0, 08 Dec
System in Full-thickness Tears (large or massive) Repair	2021
	Page: 71 of 134

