10.5 SAFETY ANALYSES

All safety endpoints will be summarized using the safety population.

Adverse Events

The number of subjects reporting: adverse events, serious adverse events, adverse device effects, serious adverse device effects, and unanticipated serious device effects will be summarized. In addition, for each adverse event, the following will be summarized: severity, the relationship to investigational device use, outcome and duration of the resolved adverse events and the duration of the adverse events at trial discontinuation.

Device deficiencies

The number of device deficiencies and the number of patients reporting a device deficiency will be summarized as well as a summary of device deficiencies with the potential to cause SADE.

Additional summaries of safety endpoints, if applicable, will be described in the SAP.

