12.1.1 Adverse Event

An Adverse Event is any untoward medical occurrence, unintended disease or untoward clinical sign (including abnormal laboratory findings) in subjects, users or other persons, whether or not causally related to the IP and whether anticipated or unanticipated.

- Note 1: This definition includes events related to the IP, comparator or ancillary products.
- Note 2: This definition includes events related to the procedures involved.
- Note 3: For users or other persons, this definition is restricted to events related to the IP

AE is used both to refer to AE which do not meet the definitions of Adverse Device Effects or Serious Adverse Events and as an umbrella term referring to adverse events of all classifications.

An AE can be any unfavorable and unintended sign (for example, an abnormal laboratory finding), symptom, or disease. For reporting purposes, emphasis is placed first and foremost on whether or not the event constitutes an untoward medical occurrence.

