12.1.4 Anticipated/Unanticipated Serious Adverse Device Effect

An Unanticipated Serious Adverse Device Effect (USADE) is a serious ADE which by its nature, incidence, severity or outcome has not been identified in the current version of the risk analysis report.

Guidance Regarding the Determination of Unanticipated Events:

During causality assessment activity, clinical judgement shall be used and the relevant documents, such as the Investigator's Brochure, the Clinical Protocol or the Risk Analysis Report shall be consulted, as all the foreseeable serious adverse events and the potential risks are listed and assessed there. The presence of confounding factors, such as concomitant medication/treatment, the natural history of the underlying disease, other concurrent illness or risk factors shall also be considered. [MEDDEV 2.7/3 Rev 3 Sec 8].

Note: An anticipated serious adverse device effect (ASADE) is an effect which by its nature, incidence, severity or outcome has been identified in the risk analysis report (see Section 4.4 for details).

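### Retear can be recorded as an adverse event and is also the primary endpoint; without AE and SAE counts that exclude it, any comparison with ARCR alone would partly restate efficacy

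*Combined protocol and SAP*

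**What the plan says.** **Retear as a complication.** Section 4.4.4 (Potential Adverse Effects) includes "infection; failure of the repair or retear; nerve damage; vascular damage" in its list. Section 12.1.4 points back to section 4.4 when it describes an anticipated serious device effect as one that "has been identified in the risk analysis report (see Section 4.4 for details".

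**What is collected.** The synopsis (Safety Data) covers "All adverse events (AEs) and complications occurring from the time of subject enrollment until study termination or study completion". Section 12.1.1 defines an AE as "any untoward medical occurrence, unintended disease or untoward clinical sign (including abnormal laboratory findings) in subjects, users or other persons", whatever the cause and whether or not it was anticipated. No section exempts the endpoint event or says how a retear found on MRI is to be recorded.

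**The same event as the endpoint.** For the primary endpoint, "Failure is defined as Sugaya Type IV or V retear/recurrence". Section 11 plans for retear rates of 30% with ARCR alone and 15% with the implant.

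**Planned safety summaries.** Section 10.5 will summarize "The number of subjects reporting: adverse events, serious adverse events, adverse device effects, serious adverse device effects", together with unanticipated serious device effects. For each adverse event it adds "severity, the relationship to investigational device use, outcome and duration of the resolved adverse events", and the duration of events still open at discontinuation. It specifies no count with retear removed or shown apart.

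**Who is in the tables.** Section 10.5 uses the safety population, and section 10.2 gives "Safety analysis set (SAF): including all patients who have received the study device". Section 5.2 nevertheless sets a safety objective against ARCR alone.

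**The concern.** A safety comparison should show whether the implant adds harm such as infection, inflammation, stiffness or anchor problems. If retears enter the AE counts and the implant halves them, the device arm gains an advantage in the AE total that is only the efficacy result counted again. A real excess of other harm could then be offset, and the arms could look equal, or the device could look safer.

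The missing recording rule adds to this. The study is not blinded (8.2.2), and investigators evaluate and record AEs (12.3). Whether an asymptomatic retear on MRI becomes an AE is left to site judgement with the arm known. The SAE count is open to the same effect, but only for retears that meet a seriousness criterion.

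**Working it through.** **The plan's own figure.** Inputs from sections 10.1 and 11: 30% v 15%, two-sided 5%, 80% power, 1:1, one interim look at 50% with O'Brien-Fleming-type spending. The fixed-design size per arm, with mean rate 0.225, is

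n = [1.960·√(2·0.225·0.775) + 0.842·√(0.30·0.70 + 0.15·0.85)]² / 0.15² = 120.5, so 121.

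An efficacy bound alone inflates this by 1.004, giving 122 per arm (244). Adding a non-binding futility bound of the same type (assumed) inflates it by 1.056, giving 128 per arm (256), within 3% of the stated 260. The sample size is not in dispute. Its rates feed the check below.

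**Retear alone.** If all retears are recorded, they put 0.30 × 130 = 39 control and 0.15 × 130 = 19.5 device subjects into the AE count.

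**Equal other harm.** Let r be the recorded retear rate and a the rate of other AEs, assumed independent. The proportion with any AE is 1 − (1 − r)(1 − a). The documents give no value for a; 20% is assumed.
- Control: 1 − 0.70·0.80 = 44.0%
- Device: 1 − 0.85·0.80 = 32.0%

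The 12-point gap is efficacy only. For a of 10% to 40% in both arms, the gap 0.15·(1 − a) runs from 13.5 to 9.0 points.

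**Unequal other harm.** With other AEs at 20% control and an assumed 28% device, the device figure is 1 − 0.85·0.72 = 38.8%. It still looks safer than control at 44.0%, despite 8 points more other harm.

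**Excess that is cancelled.** The totals are equal when the device rate of other AEs is 1 − (1 − a)(1 − r_control)/(1 − r_device). The share of retears recorded is not in the documents, so it is varied, with a = 20% in control. The last column replaces independence by the greatest possible overlap in both arms, where any-AE is the larger of r and a.

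| Share recorded | Device rate at equality | Hidden excess, independent | Hidden excess, greatest overlap |
|---|---|---|---|
| 100% | 1 − 0.80·0.70/0.85 = 34.1% | 14.1 points | 30.0 − 20 = 10.0 points |
| 75% | 1 − 0.80·0.775/0.8875 = 30.1% | 10.1 points | 22.5 − 20 = 2.5 points |
| 50% | 1 − 0.80·0.85/0.925 = 26.5% | 6.5 points | 0 |
| 25% | 1 − 0.80·0.925/0.9625 = 23.1% | 3.1 points | 0 |

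With full recording, independence and control rates of other AEs from 5% to 40%, the hidden excess runs from 16.8 to 10.6 points (about 22 to 14 subjects per 130). With retear tabulated apart, 130 per arm would give 73% power (two-sided 5%) to detect 20% v 34.1%.

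**SAEs.** Assume 10%, 25% or 50% of retears are serious and other SAEs occur in 2% to 5% of controls. The hidden excess is about 1.4, 3.7 or 7.8 points (about 2, 5 or 10 subjects per 130). For example, at 25% and 5%: 1 − 0.95·0.925/0.9625 = 8.7%, an excess of 3.7 points.

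**Longer follow-up.** The 30% and 15% are 6-month rates, while AEs are collected to study end. Section 4.1 cites 47% retear at 12 months for large tears. If that rate applied in control and were halved by the device (assumed), full recording and 20% other AEs would give 1 − 0.80·0.53/0.765 = 44.6%, a hidden excess of 24.6 points.

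**The case against.** - **The contrast is not in the planned tables.** The safety set, read literally, holds only patients who received the device, and 10.5 specifies no between-arm comparison. This stands. A reader might infer that 44% v 32% will appear in the planned output; as written, it cannot. The effect arises once ARCR-alone patients are added, which the objective in 5.2 requires.
- **Recording is not stated.** A reader might infer that every Sugaya IV or V read becomes an AE. The endpoint comes from an independent radiologist (9.2.12), AEs come from investigators (12.3), and nothing says a central read triggers an AE form. The definitions allow retear to be recorded as an AE but no section says that it must be. The full-recording figures are therefore an upper case for the given retear rates.
- **Not every retear is serious.** A reader might infer that every reoperated retear is an SAE. A criterion in 12.1.3 must be met, and 8.3.3 allows for a reoperation with no night in hospital.
- **Harm is not necessarily hidden.** AEs are coded to IMDRF Annex E (12.2), and the per-event summary in 10.5 could be laid out by event type. Retear and reoperation are reported as endpoints in their own right, data after a reoperation are presented separately (7.8.1), and section 10 defers detail to the SAP. So the documents do not support saying that harm will be concealed or that no table by event type will exist. What stands is that none of these provisions specifies a count without retear.
- **The inputs are assumed.** Other-AE rates, overlap and the share recorded are not in the documents. If retear occurs mostly in subjects who already have pain or stiffness AEs, the effect shrinks, and at half recording or less it can vanish.

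**Conclusion.** The point holds in a limited form. The definitions allow a retear to be recorded as an AE, the same event is the primary endpoint, and 10.5 specifies only all-inclusive AE and SAE subject counts. Once ARCR-alone patients are in the safety tables, those counts would carry part of the efficacy result.

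At 30% v 15% retear, with 20% other AEs in control and independence, the device excess in other AEs that would be cancelled is about 14 points with full recording, and about 3 to 10 points if 25% to 75% of retears are recorded. These sizes illustrate the mechanism and are not predictions. Which count is shown first is partly a matter of presentation. Having both is what makes the comparative safety objective answerable, and it costs little.

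**What to change.** In section 10.5 or the SAP:

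1. Define the safety set to include ARCR-alone patients.
2. Set one rule, identical in both arms, for when a retear is recorded as an AE.
3. Report AE and SAE subject counts by arm, both including and excluding retear of the index tendon and reoperation for it. Use the counts without retear to judge other harm.
4. Report retear separately from the central MRI read, outside the AE counts, so that differently ascertained events are not mixed.

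Individual safety reporting under section 12 stays in place. The cost is one AE flag, one extra table and a recorded reason for each reoperation. That reason is a site judgement made with the arm known, so the inclusive count should stay beside the exclusive one.

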5. OBJECTIVE(S)

5.1 PRIMARY OBJECTIVE

The primary objective of this study is to assess the cumulative 6 months retear rate after full-thickness ARCR augmented with REGENETEN versus ARCR alone.

CONFIDENTIAL AND PROPRIETARY

Study Protocol	Smith-Nephew
A Prospective, Multi-center, Randomized Controlled	Number:
Study to Evaluate the Safety and Efficacy of ARCR	REGENETEN.2020.01
augmented with REGENETEN™ Bioinductive Implant	Version: 2, 08 Dec 2021
System in Full-thickness Tears (large or massive) Repair versus ARCR alone	Page: 27 of 134

5.2 SECONDARY OBJECTIVE(S)

To assess safety and efficacy of full-thickness ARCR augmented with REGENETEN versus ARCR alone.

5.3 OTHER OBJECTIVE(S)

To assess safety and efficacy of full-thickness ARCR augmented with REGENETEN versus ARCR alone in at-risk-groups (diabetics, smokers, hypertensive, heavy laborer, age > 65 years);

To assess safety and efficacy of full-thickness ARCR augmented with REGENETEN in revision repair group (observational);

To generate health economic evidence.

